4.1.1.2 Decision Process for Dose Escalation and MAD Initiation

The DEC will decide dose escalation and the initiation and selection of doses for MAD cohorts based on emerging safety and tolerability data from SAD. After all subjects in a cohort have been dosed and completed study procedures through Day 15, the overall safety and tolerability of the dose will be determined after evaluation of the blinded safety data [treatment emergent adverse events (TEAEs), adverse events (AEs) of special interest, otology examinations (imaging pictures of tympanic membrane, bone conduction hearing at 1, 2, 4 kHz by PTA, TVAS, Modified Brighton Grading Scale, and vital signs] for the current cohort. Cumulative AE data from the preceding cohort(s) will also be included in the assessment for dose escalation. Details will be defined in the DEC Charter.

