6.5 Previous and Concomitant Treatment (Medication and Nonmedication Therapy)

These restrictions are required after ASP0598 Otic Solution or placebo administration on Randomization (Day 1), until completion of study procedures at Day 57 (SAD) / Day 85 (single dose expansion or MAD) / Day 113 (multiple dose expansion) or EOS visit.

- Ear drop agents will be used only for the treatment of otitis media with suppurative ear discharge. Only Ciprofloxacin or Ofloxacin ear drops (does not include steroids) are allowed to be used in the ASP0598 Otic Solution or placebo treated ear. Investigators should minimize treatment with ear drops up to a maximum of 10 days and consider alternative treatment (e.g., oral antibiotics).
- Any other topical agents in the ear canal are prohibited to use in the ASP0598 Otic Solution or placebo treated ear.
- Any otologic procedures (e.g., paper patch or surgeries) to the ASP0598 Otic Solution or placebo treated ear are prohibited.

All concomitant medication usage will be noted and recorded during each study visit.

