6.6 Dose Modification

SAD and single dose expansion

Not Applicable.

MAD

On Day 15 or Day 29, treatment can be skipped at the Investigator's discretion based on safety reasons that interrupt IP administration (e.g., ear canal skin irritation, mild otorrhea). Subjects should be encouraged to return to the office for evaluation and additional IP administration within the Day 15 or Day 29 visit windows. In the case that the investigator is unable to conduct IP administration for anything other than safety reasons, consultation with the sponsor may be required.

Multiple dose expansion

The statement above for MAD is also applicable to the multiple dose expansion. Additionally, the treatment on Day 15 or Day 29, treatment will be skipped in cases where complete closure is confirmed. If the perforation is detected on Day 29 after treatment was skipped on Day 15, IP administration can be conducted.

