7.3.6 Adverse Events of Special Interest

Incidence of adverse events of special interest as defined below:

1. Cholesteatoma or ear neoplasm
2. Ototoxic symptoms (tinnitus, sensorineural hearing loss, dizziness)
3. Otitis media or otitis externa

Additional data may be collected for AEs of special interest (i.e., unscheduled microscopic pictures, histopathology, surgical procedures, or other treatments).

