9.5 Analysis of Safety

Safety analysis will be conducted using the SAF, unless otherwise specified.

The primary endpoints to evaluate the safety and tolerability of ASP0598 Otic Solution are shown below:

- TEAEs
- Incidence of AEs of special interest:
 1. Cholesteatoma or ear neoplasm
 2. Ototoxic symptoms (tinnitus, sensorineural hearing loss, dizziness)
 3. Otitis media or otitis externa
- Change from baseline in bone conduction hearing at 1, 2, 4 kHz by PTA
- Change from baseline in TVAS

No statistical hypothesis testing will be performed.

Continuous data will be summarized using descriptive statistics and categorical data will be summarized using number and percentage of subjects.

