5 EFFICACY AND SAFETY ENDPOINTS

5.1 Primary Safety Endpoint(s)

- Treatment-emergent adverse events (TEAEs)
 - **TEAE:** an AE observed after starting administration of the study drug through end of study visit. If an AE occurs on Day 1 and the onset check box is marked “Onset after the dose of study drug” or the onset check box is left blank, then the AE will be considered TEAE. Refer to Section [6.9.1](#) for end day of end of study visit definition.
 - **Drug-related TEAE:** any TEAE with a causal relationship assessed as “yes” by the investigator. If the relationship is missing then it is considered as drug-related.

Imputed date for AE onset date may be used to determine TEAE (Section [6.9.3.1](#)).

The investigator will use the following definitions to rate the severity of each AE:

- Mild
- Moderate
- Severe

- Incidence of AEs of special interest will be defined as shown below.
 1. Cholesteatoma or neoplasm
 2. Ototoxic symptoms (tinnitus, sensorineural hearing loss, dizziness)
 3. Otitis media or otitis externa

AEs of special interest will be identified using custom MedDRA queries (CMQs). Detailed information about AEs of special interest is provided in Appendices 1, 2 and 3.

- Change from baseline in bone conduction hearing at 1, 2, 4 kHz by Pure Tone Audiometry (PTA)

A lower value indicates better level of hearing.

For the change from baseline, a negative value (decrease from baseline) indicates improvement (i.e., better level of hearing).

Mean bone conduction hearing (dB):

Arithmetic mean of the values at 1, 2 and 4 kHz. If the value is missing for any of the 3 frequencies, then the mean value will be set to missing.

- Change from baseline in Tinnitus Visual Analog Scale (TVAS)

The TVAS is a numeric scale and ranges from 0 (not at all strong or loud) to 10 (extremely strong or loud). A lower value indicates less level of discomfort.

For the change from baseline, a negative value (decrease from baseline) indicates improvement (i.e., less level of discomfort).

TVAS may be reported for one of the following areas: ear (left, right or bilateral) or other.

At a time point, if a subject did not experience tinnitus, TVAS will be reported as 0. In this case, the TVAS will be considered as 0 for all two areas.

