9 APPENDICES

9.1 Appendix 1: Pre-Specified Criteria for Adverse Events of Interest: Cholesteatoma or Neoplasm

All selected terms are based on MedDRA Version 23.0

Neoplasm

1. Aural neoplasms benign (PTs)

Preferred Term Code	Preferred Term
10052241	Aural cystadenoma
10003794	Aural polyp
10069051	Benign ear neoplasm
10004292	Benign middle ear neoplasm
10008649	Cholesterin granuloma of middle ear
10008660	Cholesterol granuloma
10061332	Paraganglion neoplasm

2. Aural neoplasms malignant (PTs)

Preferred Term Code	Preferred Term
10055016	Ear neoplasm
10055017	Ear neoplasm malignant
10082277	External ear neoplasm malignant
10061267	Malignant middle ear neoplasm

Cholesteatoma (PTs)

Preferred Term Code	Preferred Term
10008642	Cholesteatoma

9.2 Appendix 2: Pre-Specified Criteria for Adverse Events of Interest: Ototoxic symptoms (Tinnitus, Sensorineural hearing loss, Dizziness)

All selected terms are based on MedDRA Version 23.0

Ototoxicity symptoms (PTs)

Preferred Term Code	Preferred Term
10043882	Tinnitus
10047340	Vertigo
10013573	Dizziness
10011878	Deafness
10061373	Sudden hearing loss

Ototoxicity (PTs)

Preferred Term Code	Preferred Term
10033109	Ototoxicity

9.3 Appendix 3: Pre-Specified Criteria for Adverse Events of Interest: Otitis media or Otitis externa

All selected terms are based on MedDRA Version 23.0

Middle ear infections (PTs)

Preferred Term Code	Preferred Term
10061557	Allergic otitis media
10078160	Bezold abscess
10081430	Eosinophilic otitis media
10063095	Gradenigo's syndrome
10065838	Middle ear inflammation
10061302	Myringitis
10078830	Noninfective myringitis
10033078	Otitis media
10033079	Otitis media acute
10065176	Otitis media bacterial
10033081	Otitis media chronic
10065175	Otitis media fungal
10067322	Otitis media haemophilus
10033083	Otitis media moraxella
10080507	Otitis media pneumococcal
10033085	Otitis media post measles
10080508	Otitis media staphylococcal
10065177	Otitis media viral
10033102	Otosalpingitis
10034762	Petrositis

External ear infections (PTs)

Preferred Term Code	Preferred Term
10000295	Abscess of external auditory meatus
10075072	Allergic otitis externa
10014014	Ear lobe infection
10015729	External ear cellulitis
10065837	External ear inflammation
10019959	Herpes simplex otitis externa
10063491	Herpes zoster oticus
10033072	Otitis externa
10065179	Otitis externa bacterial
10033076	Otitis externa candida
10052557	Otitis externa fungal
10065178	Otitis externa viral
10062067	Perichondritis

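### The SAP Appendix 3 term list for the otitis adverse event of special interest has no Preferred Term for an ear infection of unstated site

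*SAP*

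**What the plan says.** Protocol 9.5 introduces the safety endpoints with "The primary endpoints to evaluate the safety and tolerability of ASP0598 Otic Solution are shown below". The list that follows includes AESI incidence and, separately, treatment-emergent adverse events (TEAEs) overall. The third AESI category in Protocol 7.3.6 is "Otitis media or otitis externa". Protocol 9.5.1 leaves the selection of AESI events to the SAP.

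SAP 5.1 then says "AEs of special interest will be identified using custom MedDRA queries (CMQs", and adds: "Detailed information about AEs of special interest is provided in Appendices 1, 2 and 3". Appendix 3 (SAP 9.3) covers the otitis category in two blocks, one headed "Middle ear infections (PTs" and the other its external-ear counterpart. SAP 5.1, SAP 6.5.1 and the appendix describe no medical review and no other way for an event to enter the count. SAP 6.5.1 plans an AESI overview and tables by system organ class and Preferred Term for each category, next to the same tables for all TEAEs.

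**The concern.** A query built on a fixed term list counts only events coded to a term on the list. If a site records an infection of the treated ear without saying whether the middle or the external ear is affected, and the coded term is equally unspecific, the event falls between the two blocks. The loss runs one way only, because a missing term can lower the AESI count but not raise it. The count then depends partly on how each site words its reports, in groups of 4 to 13 subjects.

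The gap also looks unintended. The list already goes well beyond plain otitis media and otitis externa, so the omission does not follow from a deliberately narrow definition, and the SAP gives no reason for it.

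**Working it through.** The documents give no figure for this point, so the check is of the content of the list, followed by simple arithmetic for scale.

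**1. What Appendix 3 contains.** The middle-ear block has 20 Preferred Terms and the external-ear block 13, so 20 + 13 = 33.

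- 20 of the 33 contain the word otitis, including plain *Otitis media* and *Otitis externa*.
- The other 13 include *Middle ear inflammation*, *External ear inflammation*, *Bezold abscess*, *Petrositis*, *Perichondritis* and *Ear lobe infection*.
- One term contains the word infection: *Ear lobe infection*, which is site-specific.
- No term is a general ear-infection term, and none contains otorrhoea, discharge or suppuration.

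**2. Comparison with Appendix 1.** The neoplasm list pairs site-specific terms (*Benign middle ear neoplasm*, *Malignant middle ear neoplasm*, *External ear neoplasm malignant*) with terms of unspecified site (*Benign ear neoplasm*, *Ear neoplasm*, *Ear neoplasm malignant*). A neoplasm reported without a site is therefore captured. Appendix 3 has no such fallback.

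**3. Tracing one event.** Take an adverse event coded to an ear infection with no site given.

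- All-TEAE tables (SAP 6.5.1): counted.
- Otitis AESI overview and tables (SAP 6.5.1): not counted, because the code is not among the 33 terms and no other route is stated.

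**4. Scale.** One subject left out of the numerator changes the group's incidence by 100/n percentage points. Group sizes are those planned in Protocol 6.3.6.

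| Group | n | 100/n (points) |
|---|---|---|
| SAD active, per cohort | 4 | 25.0 |
| MAD active, per cohort | 6 | 16.7 |
| Expansion, per group | 13 | 7.7 |

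Safety tables also show an ASP0598 total (SAP 6.5). There the effect of one subject is smaller: 100/16 = 6.25 points in SAD (4 cohorts × 4) and 100/12 = 8.3 points in MAD (2 cohorts × 6).

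The documents do not say how many events would be reported without a site, so no expected bias is calculated.

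**The case against.** The strongest reply is that little is lost. The plain otitis terms are on the list, and the investigator examines the treated ear at every visit (Protocol 6.4), by microscope (Protocol 7.1.2), so a report that does not name the site may be uncommon. An event that misses the AESI count still appears in the TEAE endpoint, which is also primary, and in its tables by Preferred Term. Whether MedDRA 23.0 has a separate unspecified-site term, and where a given verbatim would be coded, cannot be checked from these documents. All of this stands, and it limits the point to the AESI count. It does not explain why a list that counts an ear-lobe infection has no place for an unspecified ear infection.

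A reader might go further in four ways that the documents do not support.

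- **That infections the protocol acts on drop out.** The ear-drop rule ("Ear drop agents will be used only for the treatment of otitis media with suppurative ear discharge"), the escalation stopping rule (Protocol 4.1.1.3) and the treatment discontinuation criteria (Protocol 6.7 and 8.1) all name otitis media or otitis externa, and both plain terms are listed. The one unlisted trigger is discharge as an example of a reason to skip a dose, "based on safety reasons that interrupt IP administration (e.g., ear canal skin irritation, mild otorrhea". That is a sign, not an infection.
- **That otorrhoea or middle ear effusion belongs in the AESI.** Neither is part of the category as the protocol defines it, and adding them would widen the endpoint. Otorrhoea with canal erythema is already graded under the Modified Brighton scheme and summarised (SAP 6.5.4). Middle-ear mucosal inflammation with effusion is summarised there too.
- **That any event treated with the permitted ear drops should be counted.** For compliant use, the diagnosis that justifies the drops is already a listed term. For other use, the rule could label non-otitis events as otitis. It also needs a link from medication to adverse event that the documents do not show; SAP 6.2.4 only lists medications.
- **That dose-escalation decisions are affected.** The Dose Escalation Committee's data include "adverse events (AEs) of special interest, otology examinations" among other items, TEAEs among them (Protocol 4.1.1.2). Nothing says that the SAP term list governs that review.

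**Conclusion.** The point holds in a limited form. Appendix 3 is the only stated route into the otitis AESI count, and it lacks any term for an ear infection of unstated site. An event reported and coded that way would be absent from one component of the primary safety endpoint while remaining in another.

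The direction is certain: the count can only be too low. The frequency is unknown. The size per missed subject is 25.0, 16.7 or 7.7 points for groups of 4, 6 or 13, assuming the planned group sizes are reached. The conclusion also assumes that such a report would be coded to a term outside the 33. If the dictionary or the coding convention places it on a listed term, the gap closes for that event.

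**What to change.** In SAP Appendix 3, add the Preferred Terms for ear infection of unspecified site that exist in the MedDRA version used for coding. Following SAP section 1, make the change before unblinding for the interim analysis where it affects dose escalation data, and before database lock otherwise. If the omission is intended, state the reason in the appendix.

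Otorrhoea may be shown as a separate supportive row, clearly labelled as not part of the AESI count.

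The cost is a change to the appendix wording and a re-run of the query, with no new data. The downside is that a few unspecified events that are neither otitis media nor otitis externa may be counted. The tables by Preferred Term would let a reader see and separate them.
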